## 1 ZIPS Study- Trial Protocol Synopsis

|                                 |   |
|---------------------------------|---|
| Study Title                     | ZIPS Study - Zip Incision aPproximation vs. Staple
A prospective, randomized controlled post-market study to compare the use of the Zip® Surgical Skin Closure Device versus conventional staples for skin closure in subjects having undergone bilateral knee arthroplasty – Protocol No. 006  |
| Overall Objective               | The objective of this study is to evaluate the Zip Surgical Skin Closure device versus conventional steel staple placement when utilized for surgical wound closure after bi lateral unicompartmental (UNI) or bi lateral total knee replacement (TKA).   |
| Study Device                    | ZipLine Medical Inc., Zip Surgical Skin Closure Device  |
| Indication for Use              | The Zip Surgical Skin Closure Device is indicated for use during and after skin incision procedures to approximate skin and hold together the skin edges until healing can take place.  |
| Study Design                    | A prospective, non-blinded, randomized, within patient control study. A total of up to 25 subjects (targeted min. n=22) requiring bilateral knee arthroplasty (unicompartmental or total) will be enrolled. Each subject will serve as their own control, since one knee closure will be with staples, and the other knee closure with Zip device. The order of patients will be randomized to receive Zip device on one knee and steel staples on the opposing knee. |
| Number of Subjects              | A total of up to 25 patients (serving as their own control) will be enrolled. There is anticipated patient fall out (screen failures) post procedure due to surgeon not knowing which procedure is required (total or unicompartmental) until time of surgery.  |
| Number of Sites                 | ≤ 3   |
| Duration of Study               | Each enrolled subject will be followed until 6 to 8 weeks post-procedure.   |
| Primary Effectiveness Endpoints | Wound healing as judged by the CVAS (Cosmetic Visual Analogue Scale) wound healing scale – From photos taken between 6 to 8 weeks post op visit – to be judged by panel of Plastic Surgeon blinded to treatment assignments.   |

|                                   |  |
|-----------------------------------|--|
| Secondary Effectiveness Endpoints | 
 
• Surgeon evaluation including: 
 
○ Closure Method Satisfaction
 
○ Scar Satisfaction
 
○ Wound Healing as judged by the surgeon using the WES (Wound Evaluation Scale) at the 6 to 8 week final post op visit.
 
 
 
• Physical Therapist 
 
○ Range of Motion (ROM) Measurements
 
 
 
• Patient experience including: 
 
○ Pain (General Post-Operative & Incisional)
 
○ Closure Method Comfort
 
○ Closure Method Satisfaction
 
○ Scar Satisfaction
 
 
 
 |
| Primary Safety Endpoint           | The incidence and severity of adverse effects associated with Zip device and standard steel staple usage.  |
| Secondary Safety Endpoint         | None   |
| Follow-Up Schedule                | The study will be considered complete (with regard to the primary endpoint) after 22 subjects have completed the 6 to 8 - week follow up visit.  |
| Inclusion Criteria                | 
 
1. Patients 18 years of age and older;
 
2. Patients requiring epidermal closure after bi lateral total or partial (unicompartmental) knee arthroplasty;
 
3. Patients willing to be evaluated at discharge, 2 weeks, and at the 6 to 8 week post op.
 
  |
| Exclusion Criteria                | 
 
1. Known bleeding disorder not caused by medication
 
2. Known personal or family history of keloid formation or scar hypertrophy
 
3. Known allergy or hypersensitivity to non-latex skin adhesives
 
4. Atrophic skin deemed clinically prone to blistering
 
5. Any skin disorder affecting wound healing
 
6. Any other condition that in the opinion of the investigator would make a particular patient unsuitable for this study
 
   |

| Study Administration           |   |                     |
|--------------------------------|---|---------------------|
| Manager
Clinical
Affairs | [name]
[name],
[name]
[contact] | [contact] (cell) |

### 3 Introduction

#### 3.1 **Background and Rationale**

Surgical site wound closure plays a vital role in post-operative success. This effect is magnified with commonly performed elective procedures such as knee arthroplasty[1]. Sutures and staples are most commonly used based on surgeon preference and wound location. Staples are frequently used due to their deployment speed advantage over sutures. It has been suggested that the ideal method of wound/incision closure should be fast and non-traumatic, be associated with a low incidence of dehiscence and infection, and should yield acceptable cosmetic results; and while sutures and staples are presently the most common method of surgical closure, they do not demonstrate many of these properties [1,2]. Therefore, developing new methods to reduce overall treatment time while producing comparable or potentially improved cosmetic scar results and maintaining low complication rates has obvious benefits.

ZipLine Medical, Inc. has developed a novel, non-invasive skin closure device called “Zip Surgical Skin Closure” to replace sutures, staples and glue for closure of the skin layer for surgical incisions or laceration repair. The device is FDA Class I, 510(k) Exempt and began commercial use in the USA in April 2013. The device is designed to provide closure speed superior to sutures, while resulting in a suture-like cosmetic outcome. Both pre-clinical feasibility study data and feedback from over 2000 human cases during the device’s commercial use in the USA suggest that these design intentions are correct. This study will test these assertions in a controlled clinical setting, with the goal of providing results with statistical significance.

We anticipate this clinical study to be completed within 12 months from site initiation/training to site closure.

#### 3.2 **Summary of Findings from Previous Studies**

##### 3.2.1 Pre-clinical Studies

Preclinical feasibility testing of the ZipLine technology using a chronic porcine model was conducted in 2010. Surgical incisions were closed either with the ZipLine technology, or absorbable subcuticular sutures. Devices were removed at two weeks post-operatively, and resulting scars were evaluated at 6-weeks by a blinded panel of four board-certified plastic surgeons. Results revealed excellent cosmesis when compared to subcuticular suture controls.

Below is an example of comparative outcomes at 2 weeks post-op:

ZipLine Closure

Subcuticular Suture Closure

The Cosmetic Visual Analog Scale (CVAS) and ordinal Wound Evaluation Scale (WES) were used to evaluate photographs of each scar from the test subjects. Evaluators were blinded to the type of closure method used for each wound.

### Surgical Incision Closure

|           | Closure Mechanism | Avg WES | Avg CVAS |
|-----------|-------------------|---------|----------|
| Subject 1 | Controls, n=2     | 5.25    | 83.5     |
|           | ZipLine 10cm, n=4 | 5.95    | 92.75    |
| Subject 2 | Controls, n=2     | 5.90    | 84.5     |
|           | ZipLine 10cm, n=4 | 5.95    | 93.0     |

### Skin Excision Closure

[figure not shown]
|           | Closure Mechanism     | Avg WES | Avg CVAS |
|-----------|-----------------------|---------|----------|
| Subject 1 | Controls, n=2         | 5.55    | 89       |
|           | ZipLine excision, n=1 | 6.00    | 88       |
| Subject 2 | Controls, n=1         | 5.50    | 89       |
|           | ZipLine excision, n=1 | 6.00    | 88       |

These results suggest that incisions and excisions closed using ZipLine technology can result in at least equivalent cosmesis when compared to suture closure.

[figure not shown]
### Histology

Histological analysis was performed on sample scars from both test and control groups.

#### Surgical Incision Closure

[figure not shown]

Subcuticular Suture Closure

[figure not shown]

ZipLine Closure

### Skin Excision Closure

Subcuticular Suture Closure

ZipLine Closure

H&E staining was performed on representative cross-sections of incisions closed with traditional suture techniques vs. the ZipLine device. The width and depth of the resulting scars as well as the degree of local inflammatory response were evaluated by a pathologist blinded to the closure method. The degrees of scarring and inflammation were deemed to be qualitatively equivalent between the two groups.

This was an internal feasibility study and the results have not been published.

[figure not shown]
#### 3.2.2 Clinical Studies

##### Mt. Sinai School of Medicine-

A randomized, controlled, prospective post-market study was recently completed at Mt. Sinai School of Medicine's Division of Mohs, Reconstructive, and Cosmetic Surgery. The study compared suture control to an earlier variant of the Zip Surgical Skin Closure device for skin cancer excision. The manuscript has been completed and submitted to a peer-reviewed journal for publication.

Preliminary clinical study results from this study were presented at the 16th Annual Mount Sinai Winter Symposium on Advances in Medical and Surgical Dermatology which took place Dec. 6-8, 2013 in New York.

**[name].**, Chief of the Division of Mohs, Reconstructive, and Cosmetic Surgery at Mount Sinai School of Medicine, and principal investigator for the study presented the preliminary results to an audience of over 400 dermatological surgeons. He is deeply involved in minimal scar wound repair research and has done extensive research in this area of scar-less wound healing. He is currently conducting two clinical trials addressing improved scarring after surgery.

“In the study, the ZipLine device produced similar cosmetic outcomes to a traditional suture closure while significantly reducing the treatment time, which can in turn reduce the overall cost of the procedure. In addition, since with the ZipLine there are no sutures to remove, this limited the need for immediate patient return, which can benefit both the patient and clinic. The patient can instead return later when the wound is more healed,” said [name]. The preliminary data suggested a 57% reduction in wound closure procedure time when using the ZipLine device instead of sutures.

#### UC San Diego CIED (Pacemaker) Study –

A blinded, controlled and randomized study is currently underway at UC San Diego. Most cases have already been completed with promising results. A total of 40 patients underwent pacemaker or defibrillator insertions, and skin closure was randomly assigned to either subcuticular sutures or the Zip Surgical Skin Closure device. Primary endpoints for the study are closure time and cosmesis.

The Zip Surgical Skin Closure Device is an FDA Class I, 510(k) Exempt device, and no clinical studies were required for regulatory clearance. The aforementioned clinical studies are post-market studies aimed at providing statistically significant performance data regarding the Zip device.

### **3.3 Risks and Benefits**

#### **3.3.1 Risks**

Complications that may occur include:

- Allergic response
- Infection
- Dehiscence requiring intervention
- Device failure / malfunction
- Edema
- Wound site pain / discomfort
- Excessive scarring including:
  - Step-off
  - Contour irregularities
  - Excessive distortion
  - Poor cosmetic appearance

Previous evaluations have not shown any additional risks in comparison to those associated with existing wound closure methods.

#### **3.3.2 Benefits**

The potential benefits of the Zip Surgical Skin Closure device over staples include:

- Improved cosmetic outcome

- Equivalent adverse event (e.g., dehiscence, infection) occurrence
- Greater patient satisfaction
- Reduced risk of surgical site infection due to the ZIP device's non-invasive application
- Reduced number and expertise (MD vs. PA) of resources required for closure

This study is intended to measure the result of some or all of these benefits.

## 4 Device Description

### 4.1 Device Overview

ZipLine Medical, Inc. has developed a novel, non-invasive skin closure device called "Zip Surgical Skin Closure" to replace sutures, staples and glue for closure of the skin layer for surgical incisions or laceration repair. The device is designed to provide closure speed superior to sutures, while resulting in a suture-like cosmetic outcome. Both pre-clinical feasibility study data and feedback from over 2000 human cases during the device's commercial use in the USA suggest that these design intentions are correct. This study will test these assertions in a controlled clinical setting, with the goal of providing results with statistical significance.

[figure not shown]
The Zip device is a single use, sterile medical device.

**Figure 1. Zip Surgical Skin Closure Device**

[figure not shown]
The Zip Surgical Skin Closure Device is applied to clean, dry skin after deeper tension-relieving (i.e., dermal or subcutaneous) sutures have been applied.

The device adheres to the skin adjacent to an incision by use of pressure-sensitive skin adhesives. A combination of acrylic and hydrocolloid adhesives are used to provide a skin-friendly environment while providing the necessary tack to maintain skin adhesion during the recommended wear time of the device (7-14 days).

**Figure 2. Adjusting Incision Closure Tension**

The device remains on the skin for the recommended 7-14 days. During this period, patients may shower (but not soak in a tub or pool) with the device on. The device is removed by lifting the edge of the device and gently peeling along the incision, taking care not to apply stress to the incision. If there is a risk of skin stripping, an adhesive removal agent may be used during removal.

**Figure 3. Key Components of the Zip Surgical Skin Closure Device**

In addition to the pressure-sensitive adhesives, the device's closure and force distribution components are made up of polyurethane monofilament, polyethylene tape, polyester and nylon.

After application, the surgeon approximates the incision edges and tensions the wound by adjusting the ratcheting straps located along the device. Once the desired tension is achieved, the excess strap ends are trimmed with scissors, and a conventional absorptive dressing may be applied.

#### **4.2 Regulatory Status**

**The Zip Surgical Skin Closure is a FDA Class I, 510(k) Exempt device.**

In 2010, ZipLine Medical, Inc. submitted a “513(g)” request for product classification to the U.S. Food and Drug Administration (FDA). In July 2010, ZipLine Medical received a letter from the FDA indicating that FDA reviewers “believe the ZipLine 1 System falls within Title 21 of the Code of Federal Regulations (CFR) 880.5240, *Medical adhesive tape and adhesive bandage (Product Code- KGX). A Medical adhesive tape and adhesive bandage is a Class I type device, exempt from the premarket notification [510(k)] requirements of the Act, subject to the limitations of the exemption found in 21 CFR 880.9.*”

**Quality System Regulations:** The Zip Surgical Skin Closure Devices have been developed and are manufactured in full compliance with FDA Title 21 CFR Part 820 Quality System Regulations, including design controls, document controls, purchasing controls, identification and traceability, production and process controls, acceptance activities, nonconforming product, corrective and preventive action, labeling and package control, handling, storage, distribution and installation, record keeping, servicing, and statistical techniques.

**Origin of Manufacture:** The Zip® brand Surgical Skin Closure Devices are manufactured in the USA.

**Company Registration:** ZipLine Medical, Inc. is registered with the FDA in compliance with Title 21 Code of Federal Regulations (CFR) Part 807, Subparts A-D.

#### **4.3 Indication For Use**

The Zip Surgical Skin Closure Device is indicated for use during and after skin incision procedures to approximate skin and hold together the skin edges until healing can take place.

#### **4.4 Device Labeling**

The Zip Surgical Skin Closure Devices are labeled in full compliance with FDA Title 21 CFR Part 820 Quality System Regulations. Each device label includes the *device name, part number, lot number and expiration (use by) date*. The devices are provided sterile, each in a sealed pouch designed for aseptic handoff into a sterile field. The devices are provided in boxes of 10 individually packaged devices, and a copy of the device Instructions For Use (IFU) accompanies each box of 10 devices.

#### **4.5 Commercial Status and Clinical Experience**

The Zip device has been commercially available since April 2013, with over 2000 clinical cases conducted in the USA, and approximately 60% of these cases being orthopedic procedures. Feedback from these cases includes the following:

- Orthopedic surgeons generally close in several layers, including a deep dermal layer.
- Devices are typically removed at 10-14 days.
- Orthopedic surgeons have indicated that they are impressed with the ease of application at the end of a case; in some cases surgeons delegated skin closure with the Zip to an assistant, such as a Physician’s Assistant in the sterile field. They also felt that the outcomes were excellent at the time of removal.
- Orthopedic surgeons liked the ability to cut the device to match the incision size and to combine devices for longer incisions.

## 5 Study Objective

[figure not shown]
The primary objective of this post-market study is to evaluate scar appearance / cosmesis associated with the use of the Zip Surgical Skin Closure versus conventional staples when utilized for surgical wound closure after bilateral knee arthroplasty (unicompartmental or total). For safety analysis, the rate of adverse events up to 8 weeks post-surgery will be compared between the ZipLine Surgical Skin Closure and standard staples.

### 5.1 Sample Size

A total of up to 25 subjects (targeted min. n=22) requiring bilateral knee arthroplasty (unicompartmental or total) will be enrolled. There is anticipated patient fall out (screen failures) post procedure due to surgeon not knowing exactly which procedure is required (total or unicompartmental) until time of surgery. Subjects who are initially enrolled in the study and surgery results in a total knee on one side and a unicompartmental on the other side will be exited from the study and not included in the final analysis. Each subject will serve as their own control since one knee closure will be with staples, and the other knee closure with Zip device. The order of patients will be randomized to receive Zip device on one knee and steel staples on the opposing knee.

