#### 6.1.1 Inclusion Criteria

All subjects are required to meet the following inclusion criteria in order to be considered eligible for participation in this study:

|                    |   |
|--------------------|---|
| Inclusion Criteria | 

1. Patients 18 years of age and older;

2. Patients requiring epidermal closure after bi lateral total or partial (unicompartmental) knee arthroplasty;

3. Patients willing to be evaluated at discharge, 2 weeks and 6 or 8 -weeks post op.

 |
|--------------------|---|

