## 7 Written Informed Consent

Written Informed Consent must be obtained for all subjects who are potential study candidates before any study-specific tests or procedures are performed.

The medical records of patients who are scheduled in clinic may be screened to prior to consent to assess eligibility for the study. Patients who meet general entry criteria will be asked to sign the study-specific, Institutional Review Board (IRB)-approved Informed Consent form before any study-specific tests or procedures are performed.

If the patient fails to meet study eligibility criteria or the patient's eligibility changes prior to randomization, the patient will be considered a screen failure and their participation will not count toward enrollment for the study. A Screening/Enrollment Log will be maintained to document select information about candidates who fail to meet the entry criteria.

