**Table 1. Study Event Schedule**

|  | Before Procedure | Uni/TKA Procedure-Zip device or staple control Placement | Discharge 0-3 days Post Procedure | 14 days (+/-1 week) post Procedure | 6-8 weeks** (+/-4 days) post Procedure |
|--|------------------|--|-----------------------------------|------------------------------------|--|
| Study Initiation:  | X                |  |                                   |                                    |  |
| Informed Consent   | X                |  |                                   |                                    |  |
| Demographics/ Medical History  | X                |  |                                   |                                    |  |
| Clinical Status evaluation/site evaluation prior to wound closure device placement | X                |  |                                   |                                    |  |
| Inclusion / Exclusion Criteria Assessment  | X                |  |                                   |                                    |  |
| Left/Right Knee Randomization to Zip device or staples                             | X                |  |                                   |                                    |  |

|   |   |   |    |   |   |
|---|---|---|----|---|---|
| Photographs Taken   |   |   | X* | X | X |
| Adverse Events/Complications  |   | X | X  | X | X |
| Physician Evaluations (Satisfaction)  |   |   | X  |   | X |
| Physical Therapist Evaluations (ROM)  | X |   |    | X | X |
| Patient Evaluations(Pain, Comfort, Satisfaction)  | X |   | X  | X | X |
| Cosmetic outcome (CVAS, WES)  |   |   |    | X | X |
| Study Exit Form -CRF  |   |   |    |   | X |
| *Optional   |   |   |    |   |   |
| **Final visit will take place between week 6 and week 8 post surgery depending on surgeons standard visit schedule. |   |   |    |   |   |

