### 8.4.2 Randomization – Wound Closure Device Placement

All subjects will be screened for inclusion/exclusion criteria by study site personnel.

Once the screening and consent process is completed, subjects will be randomized to receive the Zip device (Treatment Group) on either the right or left knee by opening one of the sealed envelopes containing a randomization card. The subject will receive the staples (Control Group) on the opposing knee. The subject is considered enrolled into the study upon randomization and the subject disposition will be accounted for in study reports.

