### 8.4.3 Procedure

For consented subjects that meet the eligibility criteria, record the relevant data regarding their procedure. Record the following procedure information:

- Treatment and control sides
- Length of incisions
- Note: Subjects who require a total knee on one side and a unicompartmental on the other side will not be included in the final analysis and should be exited from the study.

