# **9 Statistical Considerations**

## **9.1 Analysis Populations and Data Handling Conventions**

### **9.1.1 Effectiveness Intent-to-Treat (ITT) Population**

All subjects will be included in effectiveness ITT analyses according to the randomized order of patients for treatment assignments, including the dermal closure procedure, regardless of protocol deviations.

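### Subjects found at surgery to have one total and one unicompartmental knee are already randomised, yet 5.1 and 8.4.3 drop them from the final analysis, which contradicts the ITT set and, if they were closed, the safety set

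*Combined protocol and SAP*

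**What the plan says.** Section numbers are those in the body of the protocol, which differ from its table of contents.

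- **Timing.** Table 1 lists "Left/Right Knee Randomization to Zip device or staples" in the column before the procedure. Section 8.4.2 adds: "The subject is considered enrolled into the study upon randomization and the subject disposition will be accounted for in study reports". According to 5.1 and the synopsis, the surgeon learns only at surgery whether a knee needs a total or a unicompartmental replacement.
- **Exit rule.** Section 5.1 says that a subject with a total replacement in one knee and "a unicompartmental on the other side will be exited from the study and not included in the final analysis". Section 8.4.3 says that these subjects "will not be included in the final analysis and should be exited from the study".
- **Analysis sets.** Section 9.1.1 states: "All subjects will be included in effectiveness ITT analyses according to the randomized order of patients for treatment assignments". It applies regardless of protocol deviations and makes no exception for mixed procedures. Section 9.1.3 includes in safety anyone given any part of either closure, by treatment received. Section 9.2.3 collects adverse events from closure to the final visit at 6 to 8 weeks.
- **Label.** The synopsis and 5.1 call the expected post-procedure fall-out screen failures. Section 7 uses that term for this case: "If the patient fails to meet study eligibility criteria or the patient's eligibility changes prior to randomization", and the consequence is that "the patient will be considered a screen failure and their participation will not count toward enrollment for the study".

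**The concern.** These subjects are enrolled and randomised when the mix is found, so removing them is a post-randomisation exclusion. An analyst cannot follow both 9.1.1 and the exit rule. The plan defines no modified ITT set, and the per-protocol definition in 9.1.2 is silent on them.

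The more practical worry is safety. The exit rule speaks of the final analysis without qualification, so it can be read as covering adverse events too. If a mixed subject has already been closed with Zip on one knee and staples on the other, both wounds were exposed to the study closures. Exit would end the visits at which problems with them are recorded. The incidence and severity of adverse events is the primary safety endpoint, and Section 5 sets the comparison at up to 8 weeks.

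**Working it through.** No published figure decides this point, so the check sets the passages side by side. Only the last step uses arithmetic.

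1. **Status at discovery.** Randomisation precedes the procedure (Table 1), randomisation is enrolment (8.4.2), and the mix is known only at surgery (5.1). Every mixed subject is therefore a randomised, enrolled subject. Section 5.1 itself describes them as initially enrolled.

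2. **Effectiveness set.** Under 9.1.1 the subject is in; under 5.1 and 8.4.3 the subject is out. The effect on the primary test follows from two other sections. CVAS is scored from photographs taken at the final visit (8.4.6), and 9.1.4 leaves missing data out. A subject exited at surgery has no final photograph, hence no pair. The paired t test uses the same pairs under either reading. The exclusion is also fixed in advance on procedure type and removes one Zip knee and one staple knee each time.

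3. **Safety set.** Table 1 schedules adverse event assessment at four points: procedure, discharge, 14 days, and 6 to 8 weeks. A subject closed and then exited at surgery keeps one of the four and loses three. Section 4.1 gives a recommended device wear of 7 to 14 days, so removal would fall after exit. The IFU warns of skin stripping on removal and of blistering with postoperative edema. Yet 9.1.3 keeps this subject in the safety denominator, and 9.2.3 expects events to the final visit.

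4. **What softens step 3.** Section 13.1 monitors adverse events through 3 months and asks the investigator to follow unresolved serious events, with no exception for exited subjects. Section 10 requires an exit form for every enrolled subject. None of these supplies a visit after exit, so non-serious wound events would be picked up only by chance.

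5. **Does closure come before exit?** The text does not settle it. The exit note stands in 8.4.3, ahead of the closure step in 8.4.4, which allows exit before any study closure. Section 5.1 describes the fall-out as post procedure, which makes closure before exit plausible. Figure 4, the study schematic, was not visible in the text available for this review and might bear on this.

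6. **Label.** The change-of-eligibility limb in Section 7 is tied to the time before randomisation, which has passed. The failed-criterion limb needs a criterion. The relevant one reads "Patients requiring epidermal closure after bi lateral total or partial (unicompartmental) knee arthroplasty" and does not say in terms that both knees must have the same procedure, although the synopsis objective reads that way.

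7. **How many subjects.** The documents give no mixed-procedure rate. With an assumed rate m among 25 enrolled, the expected number is 25m, and the chance of at least one is 1 − (1 − m)^25.
   - m = 5%: 25 × 0.05 = 1.25 subjects; 1 − 0.95^25 = 0.723.
   - m = 10%: 25 × 0.10 = 2.5 subjects; 1 − 0.90^25 = 0.928.

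   At these rates about 1 to 3 subjects are affected, and at least one case is more likely than not.

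**The case against.** The best reply is that a specific rule, stated in advance in two places, overrides a general sentence about protocol deviations, and that 9.1.4 makes the question moot for the primary endpoint. The second half stands: the CVAS result hardly depends on which section governs. The first half does not fully answer the point. Section 9.1.1 does not defer to 5.1, and even an override would leave unclear whether the final analysis includes safety.

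A second reply is that the safety conflict is hypothetical, because exit may come before closure, and that 9.1.3 and 13.1 already cover anyone who was closed. The conditional nature is accepted. But membership of the safety set does not produce data, and the scheduled visits that would do so end at exit.

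A third reply is that 8.1, which continues participation to the final visit, is only a general statement of duration, and that 8.6 allows for early exit. That is fair, and 8.1 is not relied on here as a separate contradiction.

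Finally, the screen-failure label might be taken to mean that these subjects do not count toward the 25. The documents do not support reading this as a real dispute over the enrolment count. Section 5.1 calls the subjects initially enrolled and mentions the fall-out directly after the figures of 25 and 22, so the natural reading is that the margin of 3 absorbs them. What remains is a wrong term.

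**Conclusion.** The conflict between 9.1.1 and the exit rule is firm and rests on the text alone. The conflict with 9.1.3 and 9.2.3 is conditional: it applies to any mixed subject who received some part of either closure before exit, which is plausible but not established. The consequence is an effectiveness set stated two ways and possibly incomplete data for the primary safety comparison, in perhaps 1 to 3 of 25 subjects at the assumed 5% to 10% rate. It should be fixed, but it does not threaten the trial's main conclusion.

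Two stronger readings should be resisted. A reader might infer that the exclusion biases the Zip–staple contrast in CVAS. The documents do not support that, because the rule is set in advance, removes one knee from each arm, and concerns subjects who would have no final photograph. A reader might also infer a loss of power. With no mixed-procedure rate in the documents, any such figure would rest wholly on assumption, and the changes below would not recover it.

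**What to change.** 1. In 5.1 and 8.4.3, limit the exclusion to the effectiveness analysis. State that any subject who received any part of either closure stays in adverse event follow-up at the scheduled visits to 6 to 8 weeks and in the 9.1.3 safety analysis.
2. Before CVAS data are available, reconcile 9.1.1 with 5.1 and 8.4.3. Name the effectiveness set without mixed pairs a modified ITT set, and show all randomised subjects in the disposition. A sensitivity result for all randomised subjects, using final-visit photographs from mixed subjects who received both closures, is optional.
3. In the synopsis and 5.1, replace the term screen failures for these randomised subjects, and say that they count toward the 25, as 8.4.2 implies.

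The cost is scheduled visits for the few subjects who would now be exited, wording changes in the synopsis, 5.1, 8.4.3 and 9.1.1, and a protocol amendment with IRB approval under 14.2 and 14.4. The closures themselves do not change.
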